6.3.5 Duration of Response

Duration of overall response: The duration of overall response is measured from the time measurement criteria are met for CR or PR (whichever is first recorded) until the first date that recurrent or progressive disease is objectively documented (taking as reference for progressive disease the smallest measurements recorded since the treatment started).

The duration of overall CR is measured from the time measurement criteria are first met for CR until the first date that progressive disease is objectively documented.

Duration of stable disease: Stable disease is measured from the start of the treatment until the criteria for progression are met, taking as reference the smallest measurements recorded since the treatment started, including the baseline measurements.

6.3.6 Progression-Free Survival

PFS is defined as the duration of time from start of each treatment to time of progression or death, whichever occurs first.

6.3.7 Response Review

Simultaneous review of the patients' files and radiological images for all responses will be reviewed by an expert(s) independent of the study at the study's completion.

6.4 TOXICITY CRITERIA

The following adverse event management guidelines are intended to ensure the safety of each patient while on the study. The descriptions and grading scales found in the revised NCI Common Terminology Criteria for Adverse Events (CTCAE) version 4.0 will be utilized for AE reporting. All appropriate treatment areas should have access to a copy of the CTCAE version 4.0. A copy of the CTCAE version 4.0 can be downloaded from the CTEP web site (http://ctep.cancer.gov/protocolDevelopment/electronic_applications/ctc.htm#ctc_40).

7 SAFETY REPORTING REQUIREMENTS/DATA AND SAFETY MONITORING PLAN

7.1 DEFINITIONS

7.1.1 Adverse Event

Any untoward medical occurrence in a human subject, including any abnormal sign (for example, abnormal physical exam or laboratory finding), symptom, or disease, temporally associated with the subject's participation in research, whether or not considered related to the subject's participation in the research.

7.1.2 Suspected adverse reaction

Suspected adverse reaction means any adverse event for which there is a reasonable possibility that the drug caused the adverse event. For the purposes of IND safety reporting, 'reasonable possibility' means there is evidence to suggest a causal relationship between the drug and the adverse event. A suspected adverse reaction implies a lesser degree of certainty about causality than adverse reaction, which means any adverse event caused by a drug.

7.1.3 Unexpected adverse reaction

An adverse event or suspected adverse reaction is considered “unexpected” if it is not listed in the investigator brochure or is not listed at the specificity or severity that has been observed; or, if an investigator brochure is not required or available, is not consistent with the risk information described in the general investigational plan or elsewhere in the current application. “Unexpected” also refers to adverse events or suspected adverse reactions that are mentioned in the investigator brochure as occurring with a class of drugs or as anticipated from the pharmacological properties of the drug but are not specifically mentioned as occurring with the particular drug under investigation.

7.1.4 Serious

An Unanticipated Problem or Protocol Deviation is serious if it meets the definition of a Serious Adverse Event or if it compromises the safety, welfare or rights of subjects or others.

7.1.5 Serious Adverse Event

An adverse event or suspected adverse reaction is considered serious if in the view of the investigator or the sponsor, it results in any of the following:

- Death,
- A life-threatening adverse drug experience
- Inpatient hospitalization or prolongation of existing hospitalization
- Persistent or significant incapacity or substantial disruption of the ability to conduct normal life functions
- A congenital anomaly/birth defect.
- Important medical events that may not result in death, be life-threatening, or require hospitalization may be considered a serious adverse drug experience when, based upon appropriate medical judgment, they may jeopardize the patient or subject and may require medical or surgical intervention to prevent one of the outcomes listed in this definition.

7.1.6 Disability

A substantial disruption of a person’s ability to conduct normal life functions.

7.1.7 Life-threatening adverse drug experience

Any adverse event or suspected adverse reaction that places the patient or subject, in the view of the investigator or sponsor, at immediate risk of death from the reaction as it occurred, i.e., it does not include a reaction that had it occurred in a more severe form, might have caused death.

7.1.8 Protocol Deviation (NIH Definition)

Any change, divergence, or departure from the IRB-approved research protocol.

7.1.9 Non-compliance (NIH Definition)

The failure to comply with applicable NIH Human Research Protections Program (HRPP) policies, IRB requirements, or regulatory requirements for the protection of human research subjects.

7.1.10 Unanticipated Problem

Any incident, experience, or outcome that:

- Is unexpected in terms of nature, severity, or frequency in relation to
 - (a) the research risks that are described in the IRB-approved research protocol and informed consent document; Investigator's Brochure or other study documents, and
 - (b) the characteristics of the subject population being studied; AND
- Is related or possibly related to participation in the research; AND
- Suggests that the research places subjects or others at a *greater risk of harm* (including physical, psychological, economic, or social harm) than was previously known or recognized.

7.2 NIH INTRAMURAL IRB AND CLINICAL DIRECTOR REPORTING

7.2.1 NIH Intramural IRB and NCI CD Expedited Reporting of Unanticipated Problems and Deaths

The Protocol PI will report in the NIH Problem Form to the NIH Intramural IRB and NCI Clinical Director:

- All deaths, except deaths due to progressive disease
- All Protocol Deviations
- All Unanticipated Problems
- All non-compliance

Reports must be received within 7 days of PI awareness via iRIS.

7.2.2 NIH Intramural IRB Requirements for PI Reporting at Continuing Review

The protocol PI will report to the NIH Intramural IRB:

1. A summary of all protocol deviations in a tabular format to include the date the deviation occurred, a brief description of the deviation and any corrective action.
2. A summary of any instances of non-compliance
3. A tabular summary of the following adverse events:
 - All Grade 2 **unexpected** events that are possibly, probably or definitely related to the research;
 - All Grade 3 and 4 events that are possibly, probably or definitely related to the research;
 - All Grade 5 events regardless of attribution;
 - All Serious Events regardless of attribution.

NOTE: Grade 1 events are not required to be reported.

7.2.3 NIH Intramural IRB Reporting of IND Safety Reports

Only IND Safety Reports that meet the definition of an unanticipated problem will need to be reported to the NIH Intramural IRB.

7.3 SAFETY REPORTING CRITERIA TO THE PHARMACEUTICAL COLLABORATORS

7.3.1 Novartis

The Principal Investigator will notify Novartis of each Serious Adverse Event (SAE) as defined under 21 CFR 310.305 encountered in the Clinical Trial within 24 hours of becoming aware of it. This applies to SAEs which occur after the patient takes the first dose of study drug and continues until at least 30 days after the patient has stopped study treatment or until the patient is taken off-study, whichever comes first. Information about all SAEs is collected and recorded on the Novartis Serious Adverse Event Report Form; all applicable sections of the form must be completed in order to provide a clinically thorough report. The PI must assess and record the relationship of each SAE to each specific study treatment, complete the SAE Report Form and send the completed, signed form along with the Novartis provided fax cover sheet to the Novartis Oncology Drug Safety and Epidemiology (DS&E) department by [contact]) or email ([contact]) within 24 hours of PI's awareness. To ensure patient safety, each pregnancy occurring while the patient is on study treatment must be reported to Novartis within 24 hours of learning of its occurrence. The pregnancy should be followed up to determine outcome, including spontaneous or voluntary termination, details of the birth, and the presence or absence of any birth defects, congenital abnormalities, or maternal and/or newborn complications.

Pregnancy should be reported by the investigator to the oncology Novartis Drug Safety and Epidemiology Department (DS&E) by [contact]) or email ([contact]). Pregnancy follow-up should include an assessment of the possible relationship to the investigational/study treatment and any pregnancy outcome. Any SAE experienced during pregnancy must be reported on the SAE Report Form.

Pregnancy outcomes must be collected for the female partners of any males who took study treatment in this study. Consent to report information regarding these pregnancy outcomes should be obtained from the mother.

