The potential reproductive risk for humans is unknown. However, due to the observed malformations in rats, everolimus should be considered potentially teratogenic. Everolimus should not be given to pregnant women unless the potential benefit outweighs the potential risk for the fetus. Women of childbearing potential should be advised to use highly effective contraception methods while they are receiving everolimus and up to 8 weeks after treatment has been stopped. It is not known whether everolimus is excreted in human milk. In animal studies, everolimus and/or its metabolites were readily transferred into the milk of lactating rats. Therefore women who are taking everolimus should not breastfeed.

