- 2.1.1.8 Fasting serum cholesterol ≤ 300 mg/dL OR ≤ 7.75 mmol/L AND fasting triglycerides ≤ 2.5 x ULN. NOTE: In case one or both of these thresholds are exceeded, the patient can only be included after initiation of appropriate lipid lowering medication;
- 2.1.1.9 Women of childbearing potential (WOCBP) or partners of WOCBP participating in this study must agree to use highly effective contraception while on treatment and for at least 8 weeks after end of treatment, because the effects of sunitinib and everolimus on the developing human fetus are unknown. Should a woman become pregnant or suspect she is pregnant while she or her partner is participating in this study, she should inform her treating physician immediately.

Highly effective contraception methods include combination of:

- a. Any two of the following:
 - Use of oral, injected or implanted hormonal methods of contraception or;
 - Placement of an intrauterine device (IUD) or intrauterine system (IUS);
 - Barrier methods of contraception: condom or occlusive cap (diaphragm or cervical/vault caps) with spermicidal foam/gel/film/cream/ vaginal suppository;
- b. Total abstinence or;
- c. Male/female sterilization.

Women are considered post-menopausal and not of child-bearing potential if they have had 12 months of natural (spontaneous) amenorrhea with an appropriate clinical profile (e.g. age appropriate, history of vasomotor symptoms) or have had surgical bilateral oophorectomy (with or without hysterectomy) or tubal ligation at least six weeks prior to enrollment. In the case of oophorectomy alone, only when the reproductive status of the woman has been confirmed by follow up hormone level assessment is she considered not of child-bearing potential.

- 2.1.1.10 Must have fully recovered from toxicities of any prior treatment with cytotoxic drugs, radiotherapy, surgery, or other anti-cancer modalities (returned to baseline status as noted before most recent treatment or \leq grade 1).
- 2.1.1.11 Ability of subject to understand and the willingness to sign a written informed consent document.

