Cycle 2	Day 1 within 1 week prior to treatment or cross-over treatment	
 • Clinical assessment³ • CBC, Chemistries², free T4, T3, TSH • Urinalysis • 12 lead ECG • Concomitant Medications • Adverse Events • Urine or serum HCG in women of childbearing potential (within 3 days before study drug initiation)
	Day 15 within 1 week prior to treatment	
 • CBC, • Chemistries, • Urinalysis • Concomitant Medications • Adverse Events
Cycle N	Day 1 within 1 week prior to treatment or cross-over treatment	
 • Clinical assessment³ • CBC, Chemistries², free T4, T3, TSH • Chromogranin A (every 3 months) • Urinalysis • 12 lead ECG • Concomitant Medications • Adverse Events • Radiological evaluation of treatment response⁵ • Urine or serum HCG in women of childbearing

		potential (within 3 days before study drug initiation)
Safety Follow Up Visit (approximately 30 days after last dose of study drug)		

 • Clinical assessment³ • CBC, Chemistries², free T4, T3, TSH • Urine or serum HCG in women of childbearing potential • Urinalysis • Radiological evaluation of treatment response⁵ (not applicable for patients that have progressed on 2 drugs) • Concomitant Medications • Adverse Events 		
Long Term Follow up		
Telephone contact or e-mail every 3 months to determine anti-cancer therapy and survival status		

¹ Radiological Evaluations to be completed as part of the screening.

- Brain MRI or CT (if clinically indicated)
- 68-Gallium DOTATATE scan per PI discretion
- Contrast CT scan or MRI of the chest, abdomen and pelvis (CT C/A/P)
- Bone scan for patients in whom bone metastases are suspected
- FDG PET scan

² Chemistries: Sodium (Na), Potassium (K), Chloride (Cl), Total CO₂ (bicarbonate), Creatinine, Glucose, Urea nitrogen (BUN), Albumin, Calcium total, Alkaline Phosphatase, ALT/GPT, AST/GOT, Total Bilirubin, Total Protein

³ Clinical assessments: Complete history (screening only) and physical examination including height (screening only), weight, vital signs and ECOG

⁴ Filling out of the advanced directives will be offered, but obtaining of it is not required. For details see Section **10.3**

⁵ A CT or MRI of the chest/abdomen/pelvis to reassess treatment response will be done every 3 months after treatment initiation

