13.2 APPENDIX B: PREGNANCY AND ASSESSMENTS OF FERTILITY

There are no adequate data from the use of everolimus in pregnant women. Studies in animals have shown reproductive toxicity effects including embryo-toxicity and fetotoxicity. The potential risk for humans is unknown. Everolimus should not be given to pregnant women unless the potential benefit outweighs the potential risk to the fetus. If a pregnancy occurs while on study treatment, the newborn will be followed for at least 12 months.

It is not known whether everolimus is excreted in breast milk. However, in animal studies everolimus and/or its metabolites readily passed into the milk of lactating rats. Women taking everolimus should therefore not breast-feed.

Women of childbearing potential

Women of child-bearing potential, defined as all women physiologically capable of becoming pregnant, must use highly effective contraception during the study and for 8 weeks after stopping treatment. Highly effective contraception is defined as either:

- Total abstinence: When this is in line with the preferred and usual lifestyle of the subject. [Periodic abstinence (e.g., calendar, ovulation, symptothermal, post-ovulation methods) and withdrawal are not acceptable methods of contraception]
- Sterilization: have had surgical bilateral oophorectomy (with or without hysterectomy) or tubal ligation at least six weeks before taking study treatment. In case of oophorectomy alone, only when the reproductive status of the woman has been confirmed by follow up hormone level assessment
- Male partner sterilization (with the appropriate post-vasectomy documentation of the absence of sperm in the ejaculate). [For female subjects on the study, the vasectomised male partner should be the sole partner for that subject].
- Use of a combination of any two of the following (a+b or a+c or b+c):
 - a. Use of oral, injected, implanted or other hormonal methods of contraception
 - b. Placement of an intrauterine device (IUD) or intrauterine system (IUS)
 - c. Barrier methods of contraception: Condom or Occlusive cap (diaphragm or cervical/vault caps) with spermicidal foam/gel/film/cream/vaginal suppository
- In case of use of oral contraception, women should have been stable on the oral agent before taking study treatment.

Male Contraception

Sexually active males must use a condom during intercourse while taking the drug and for 8 weeks after stopping treatment and should not father a child in this period.

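### For treated women, everolimus pregnancy reporting and newborn follow-up stop with study treatment, although the protocol's own contraception period runs 8 weeks longer

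*Combined protocol and SAP*

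**What the plan says.** **The precaution period.** Section 1.2.2.2 calls everolimus potentially teratogenic and recommends, for any woman who could become pregnant, "highly effective contraception methods while they are receiving everolimus and up to 8 weeks after treatment has been stopped". Section 2.1.1 (item 2.1.1.9) makes this an entry condition: such women, and partners of such women, "must agree to use highly effective contraception while on treatment and for at least 8 weeks after end of treatment". The reason given is "because the effects of sunitinib and everolimus on the developing human fetus are unknown". Appendix B repeats that women "must use highly effective contraception during the study and for 8 weeks after stopping treatment". It tells sexually active men to use a condom "while taking the drug and for 8 weeks after stopping treatment and should not father a child in this period".

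**The reporting and follow-up triggers.** Section 7.3.1 says "each pregnancy occurring while the patient is on study treatment must be reported to Novartis within 24 hours of learning of its occurrence". Appendix B says: "If a pregnancy occurs while on study treatment, the newborn will be followed for at least 12 months".

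**Detection.** The study calendar (section 3.4) lists a urine or serum HCG test at the safety visit, about 30 days after the last dose. After that the calendar provides only: "Telephone contact or e-mail every 3 months to determine anti-cancer therapy and survival status". Section 3.1.2 describes the same content for long-term follow-up.

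**Related provisions.** Section 7.3.1 also requires pregnancy outcomes for the female partners of men who took study treatment, with no time limit. Section 7.3.2 requires each pregnancy to be reported to the sunitinib manufacturer, again with no on-treatment limit. Item 2.1.1.9 asks a woman to tell her physician at once if she becomes pregnant, or suspects it, while she or her partner is participating.

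**The concern.** The 8-week contraception period exists because exposure of a fetus around or after the last dose is thought to carry risk. If contraception fails in that period, the resulting pregnancy is one the precaution was meant to prevent, and its outcome is the safety information one would want. As written, the rules do not require such a pregnancy in a treated woman to reach the everolimus manufacturer, and they do not require her newborn to be followed. If she conceives after the safety visit, no scheduled test or question would bring it to light.

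What is at stake is completeness of reproductive safety information. The progression-free survival analysis, its power and its error rate are not involved.

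**Working it through.** The plan states no figure to reproduce. The check sets the windows side by side for a treated woman and counts days from her last study drug.

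**Inputs**
- Contraception period after treatment: 8 weeks (sections 1.2.2.2 and 2.1.1, Appendix B).
- Reporting trigger, everolimus manufacturer: on study treatment (section 7.3.1).
- Newborn follow-up trigger: on study treatment (Appendix B).
- Last scheduled HCG test: about day 30 (section 3.4).
- Visit window: up to 7 days either side of the scheduled day (section 3.4). That it applies to the safety visit is an assumption.
- Next contact: 3-monthly, covering therapy and survival only (sections 3.1.2 and 3.4).

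**Step 1: length of the period.** 8 × 7 = 56 days.

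**Step 2: days covered by the two triggers.** Both end with study treatment, so a pregnancy beginning on any of days 1 to 56 lies outside them: 0 of 56 days covered. A pregnancy that began on treatment and is found at the day-30 test is still inside both triggers.

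**Step 3: days after the last scheduled test.**
- Test on day 30: 56 − 30 = 26 days, and 26/56 = 46%.
- Test as late as day 30 + 7 = 37: 56 − 37 = 19 days, and 19/56 = 34%.
- Test as early as day 30 − 7 = 23: 56 − 23 = 33 days, and 33/56 = 59%.

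The visit is described as approximate, so the range is a better summary than 26 days alone.

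**Step 4: cross-over.** A woman who moves from everolimus to sunitinib is on study treatment again once the second drug starts, and both triggers apply again. Section 3.1.1 allows up to 3 months between drugs, and the documents do not say whether that break counts as being on study treatment. The calendar lists an HCG test before study drug initiation, including cross-over treatment, so for the break the open question is the triggers rather than the testing. The full gap, in triggers and testing together, opens after the last study drug.

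**Step 5: does another rule close the gap?** Item 2.1.1.9 may bring a post-treatment pregnancy to the site's attention, since ending treatment is not itself an off-study criterion in section 3.5.2. Neither section 7.3.1 nor Appendix B then requires a report to the everolimus manufacturer or newborn follow-up. The later sentence in section 7.3.1 on how the investigator reports a pregnancy gives the route and does not lengthen the window.

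**The case against.** The strongest reply is that much of this ground is already covered, and several wider readings do fail.

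- *A reader might infer that partner pregnancies are missed too.* Section 7.3.1 does not support that. Its sentence on outcomes in female partners has no time limit, so the 0-of-56-days result applies to treated women only.
- *A reader might infer that the two manufacturers' clauses contradict each other.* They do not. They are separate duties to separate companies and can both be met. Because section 7.3.2 covers each pregnancy, a post-treatment pregnancy known to the site would still be reported to one manufacturer. The agreement with the everolimus manufacturer (section 9.1) is not part of the documents, so whether it fixes the narrower wording cannot be judged.
- *A reader might infer that the gap covers all 8 weeks after the last everolimus dose in every patient.* Cross-over limits this, as shown in step 4.
- *A reader might infer that such a pregnancy could not come to light.* Item 2.1.1.9 provides an unscheduled route through the woman herself. What is missing is a scheduled test or question.
- *The 8 weeks is a contraception period, and nothing says reporting must span it.* This is true. The protocol does not name a fetal-risk window, and matching the two periods is a judgement. But the protocol justifies the period by unknown effects on the fetus, and it gives no reason for ending reporting and newborn follow-up sooner.

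What stands after these points is the narrow gap: treated women, after the last study drug or in a break before cross-over.

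**Conclusion.** The point holds in this limited form. For treated women, the everolimus reporting trigger and the newborn follow-up trigger cover none of the 56-day post-treatment contraception period, and about 19 to 33 of those days come after the last scheduled test with no later pregnancy question.

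This rests on reading the on-treatment wording literally and, for the range, on applying the 7-day visit window to the safety visit. The documents do not give the number of women of childbearing potential, so the expected number of affected pregnancies cannot be calculated. The Appendix B newborn sentence does not say whether it extends to partner pregnancies, and no conclusion is drawn on that.

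It is a minor improvement to safety reporting. It does not bear on the efficacy analyses.

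**What to change.** Reconcile the reporting trigger in section 7.3.1 and the newborn follow-up trigger in Appendix B with the 8-week post-treatment period that the protocol already states, and say how a break before cross-over is to be treated. Leave the sentence on outcomes in female partners at least as broad as it is now.

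Add one pregnancy question to the first 3-monthly long-term contact. With 3 months between contacts, that call or e-mail falls after day 56, so a single question covers the rest of the period.

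The cost is two wording changes, one question in a contact already planned, and an occasional extra report with outcome follow-up. No dose, treatment or contraception rule changes.
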